9.3 Demographics and Baseline Characteristics

Demographic and baseline characteristics will be listed by subject and summarized. Descriptive summary statistics (sample size, mean, median, SD, and range, when appropriate) will be provided for the continuous variables such as age, weight, height and BMI. Count and percentage will be reported for categorical variables such as sex, race, and ethnicity.

Listings will be provided for these parameters for all patients.

9.4 Prior and Concomitant Medications

Prior and concomitant medications will be coded using the World Health Organization (WHO) Drug Dictionary (Version 201506 or higher). Prior medications are drugs and therapies used before the first dose date. Medications or therapies are considered concomitant if exposure occurs after the first dose date. The number and percentage of patients with concomitant medications will be presented alphabetically by anatomical therapeutic chemical (ATC) class and by decreasing order of frequency of preferred terms within each ATC class for the safety population. Patients taking the same medication multiple times will be counted once per medication.

All medications recorded on the case report form will be listed.

9.5 Medical History

Medical history will be coded using the Medical Dictionary for Regulatory Activities (MedDRA V17.0 or higher). Medical history will be summarized by System of Organ Class (SOC) and Preferred Term (PT) for safety population. All medical history data will be provided in a listing.

9.6 Immunogenicity Analyses

Immunogenicity data will be analyzed based on the PP population by visit for all visits through 20 weeks with immunogenicity data collected.

The SPR will be estimated. The associated 2-sided 95% confidence interval will be calculated using the Clopper-Pearson method.

Proportion of subjects with anti-HBs concentration ≥ 100 mIU/mL and associated 2-sided 95% confidence interval will also be calculated using Clopper-Pearson methods.

Anti-HBs geometric mean concentration (GMC) and associated 2-sided 95% confidence interval will be calculated by exponentiating the mean and confidence interval in \log_{10} of the anti-HBs concentration assuming Normal distribution.

Analyses based on the mITT population may also be conducted.

9.7 Safety Analyses

Vaccine exposure and compliance will be summarized descriptively for safety population.

Safety data will be analyzed descriptively and will be based on the safety population. The most important safety parameters will be presented for all sites combined. Summary statistics will be used to describe the incidence of all post-injection reactions and MAEs (including SAEs, deaths, AMIs, and AESIs; further details regarding safety reporting of AMIs and AESIs are provided in Protocol Section 9.4.7.2). The incidence and proportion of post-

injection reactions and MAEs will be summarized. MAEs will be coded using the MedDRA SOC and PT.

The incidence of AMIs and major adverse cardiovascular events will be analyzed in subjects initiating hemodialysis after enrollment in the study and in subjects undergoing hemodialysis at the time of enrollment in the study.

The treatment-emergent period is defined in [Section 7.1](#).

Local and systemic post-injection reactions are to be recorded on the subject diary. If they persist longer than 7 days (i.e., 8 days or longer) and are medically attended (i.e., subject seeks medical attention), they should also be recorded and reported as MAEs, per protocol Section 10.2. The severity of the post-injection reactions will be graded using the Toxicity Grading Scale for Healthy Adult and Adolescent Volunteers Enrolled in Preventive Vaccine Clinical Trials.

Local reactions include redness, swelling and pain, and systemic reactions include malaise (not feeling well), headache, myalgia (body aches) and fatigue (feeling tired).

Post-injection reactions reported from day 1 to day 7 will be summarized by maximal severity and by vaccine group. The severity of local reactions, including redness and swelling will be categorized as none, 1 to ≤ 10 mm, >10 mm to ≤ 25 mm, >25 to ≤ 50 mm, >50 to ≤ 100 mm and >100 mm (severe local reactions).

The severity of pain and systemic reactions including malaise, headache, myalgia and fatigue occurring up to 7 days after each vaccination will be categorized as none, mild (no interference with activity), moderate (some interference with activity), severe (significant, prevents daily activity).

Temperature will be categorized as $<38^{\circ}\text{C}$ (no fever), $38\text{-}38.4^{\circ}\text{C}$, $38.5\text{-}38.9^{\circ}\text{C}$, $39\text{-}40^{\circ}\text{C}$ and $>40^{\circ}\text{C}$.

Each local and systemic reaction will also be categorized as none vs. any.

All MAEs will be coded to preferred term and system organ class using MedDRA 17.0 or higher. An MAE that started or increased in severity during the treatment-emergent period will be considered a TEMAЕ. Severity of TEMAЕs and laboratory abnormalities will be graded based on the United States Food and Drug Administration's (FDA) Guidance for Industry: Center for Biologics Evaluation and Research (CBER) Toxicity Grading Scale for Healthy Adult and Adolescent Volunteers Enrolled in Preventive Vaccine Clinical Trials (with the exception of malaise, which will be graded per CTCAE v4.03), with the modification that, by convention, all fatal MAEs will be graded as Grade 5 (Fatal). All MAEs not listed in the CBER toxicity grading scale will be graded as shown in Table 9-1.

Table 9-1: Grading Scale for Medically-Attended Adverse Events Not Included in the CBER Guidance on Toxicity Grading for Healthy Volunteers in Vaccine Clinical Trials

MAE Severity	Definition
Grade 1 – Mild	No interference with activity
Grade 2 – Moderate	Some interference with activity, not requiring medical intervention
Grade 3 – Severe	Prevents daily activity and requires medical intervention
Grade 4 – Potentially life-threatening	Emergency room visit or hospitalization
Grade 5	Death

A study vaccine-related TEMAЕ is defined as any TEMAЕ with at least a possible relationship to the study vaccine as assessed by the investigator or that is missing the assessment of causal relationship whose relationship to the study vaccine could not be ruled out.

Patients with multiple occurrences of events for a given preferred term, system organ class, or overall will only be counted once at the worst severity and strongest relationship to study vaccine for each preferred term, system organ class, and overall, respectively. MAEs that are continuous but change in grade, relationship, or seriousness will be counted as 1 event. TEMAЕs of unknown severity will be categorized separately. A TEMAЕ of unknown relationship will be considered to be probably related to study vaccine.

Incidence and percentages of subjects experiencing each reaction will be presented by severity. Summary tables showing the occurrence of any local or systemic reaction overall and at each time point will also be presented.

Tabular summaries including numbers and percentages of the following adverse events will be provided:

- All TEMAЕs
- TEMAЕs of Grade 3 or above
- All treatment-related MAEs
- Treatment-related MAEs of Grade 3 or above
- All treatment-emergent SAEs
- All treatment-related SAEs
- All TEMAЕs leading to premature discontinuation of HEPLISAV
- All SAEs leading to death
- All AMI

- All AESI

Listings will be provided for all TEAEs.

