#### **9.4.6 Post-injection Reaction Assessments**

Assessments of post-injection reactions will be collected for a minimum of 30 minutes following each of the HEPLISAV-B injections at the clinical site and as reported by the subject in a diary for 7 days. Information about the presence and severity of post-injection local (injection site) reactions (redness, swelling, and pain at or near the injection site) and systemic reactions (malaise, headache, myalgia, and fatigue) that are listed in the subject diary are considered solicited post-injection reactions. Oral temperature is also collected. Solicited post-injection reactions are related to treatment and recorded for 7 days following each study injection, including the day of injection. Post-injection reactions documented by the subject will be collected, reviewed by the study nurse/coordinator with the subject, and recorded on the appropriate eCRF. The grading criteria for post-injection reactions are in [Appendix 3](#). Further information is provided in the Study Reference Manual.

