**17. PATIENT COUNSELING INFORMATION**

- Inform vaccine recipient of the potential benefits and risks associated with vaccination, as well as the importance of completing the immunization series.
- Emphasize that HEPLISAV-B contains non-infectious purified HBsAg and cannot cause hepatitis B infection.
- Advise vaccine recipient to report any adverse events to their healthcare provider or to the Vaccine Adverse Event Reporting System (VAERS) at [name] and [www.vaers.hhs.gov](http://www.vaers.hhs.gov).
- Provide the Vaccine Information Statements, which are available free of charge at the Centers for Disease Control and Prevention (CDC) website ([www.cdc.gov/vaccines](http://www.cdc.gov/vaccines)).

© 2018, Dynavax Technologies Corporation.  
All rights reserved.

Manufactured by:  
Dynavax Technologies Corporation  
Berkeley, CA 94710 USA

US-18-00-00015

**APPENDIX 3: TOXICITY GRADING SCALE FOR HEALTHY ADULT AND ADOLESCENT VOLUNTEERS ENROLLED IN PREVENTIVE VACCINE CLINICAL TRIALS**

Local Reaction to Injectable Product	Mild (Grade 1)	Moderate (Grade 2)	Severe (Grade 3)	Potentially Life Threatening (Grade 4)
Erythema/Redness a	2.5 – 5 cm	5.1 – 10 cm	> 10 cm	Necrosis or exfoliative dermatitis
Induration/Swelling b	2.5 – 5 cm and does not interfere with activity	5.1 – 10 cm or interferes with activity	> 10 cm or prevents daily activity	Necrosis
Pain	Does not interfere with activity	Repeated use of non-narcotic pain reliever > 24 hours or interferes with activity	Any use of narcotic pain reliever or prevents daily activity	Emergency room (ER) visit or hospitalization
Fever c (°C) (°F)	38.0 – 38.4 100.4 – 101.1	38.5 – 38.9 101.2 – 102.0	39.0 – 40 102.1 – 104	> 40 > 104
Malaise	Uneasiness or lack of well being	Uneasiness or lack of well being; limiting instrumental ADL	A grade is not available	A grade is not available
Headache	No interference with activity	Repeated use of non-narcotic pain reliever > 24 hours or some interference with activity	Significant; any use of narcotic pain reliever or prevents daily activity	ER visit or hospitalization
Myalgia	No interference with activity	Some interference with activity	Significant: prevents daily activity	ER visit or hospitalization
Fatigue	No interference with activity	Some interference with activity	Significant: prevents daily activity	ER visit or hospitalization

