Sources: ([Center for Biologics Evaluation and Research 2007](#), [National Cancer Institute 2010](#)).

a In addition to grading the measured local reaction at the greatest single diameter, the measurement should be recorded as a continuous variable.

b Induration/swelling should be evaluated and graded using the functional scale as well as the actual measurement.

c Oral temperature; no recent hot or cold beverages or smoking. Subject should be at rest for vital sign measurements.

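### SAP 9.7 names the Appendix 3 toxicity scale, but its reaction categories omit the functional grade for swelling and have no Grade 4 except for fever

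*SAP*

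**What the plan says.** SAP 9.7 names its scale: "The severity of the post-injection reactions will be graded using the Toxicity Grading Scale for Healthy Adult" and adolescent volunteers. The SAP does not cite an appendix number. The link comes from the protocol, where 9.4.6 states "The grading criteria for post-injection reactions are in" Appendix 3, and 10.1 names the same scale with the same appendix.

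For tabulation, SAP 9.7 then sets its own categories:

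- Redness and swelling: "The severity of local reactions, including redness and swelling will be categorized as none", then five diameter bands. The last is ">100 mm (severe local reactions").
- Pain, malaise, headache, myalgia and fatigue: these "will be categorized as none, mild (no interference with activity), moderate (some interference with activity), severe (significant, prevents daily activity").
- Temperature: below 38, 38–38.4, 38.5–38.9, 39–40 and above 40 °C.

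Later in the same section: "Incidence and percentages of subjects experiencing each reaction will be presented by severity". No further categories are given there.

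In Appendix 3, Grade 3 swelling is "> 10 cm or prevents daily activity", and footnote b adds: "Induration/swelling should be evaluated and graded using the functional scale as well as the actual measurement".

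**The concern.** One section adopts a grading scale and then specifies output in which that scale cannot be read. If the tables follow the written categories, a swelling that is severe because of what it stops the patient doing appears only by its size. A non-fever reaction that reached Grade 4 cannot be shown as Grade 4. The regimen has four doses, and the package insert in Appendix 2 says that safety in adults on hemodialysis has not been established, so readers will look to these tables for the most severe reactions. Protocol 8.1 also lists a Grade 4 reaction within 7 days as a reason to stop injections, so the report should be able to show how many there were.

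**Working it through.** There is no plan figure to reproduce. The check sets SAP 9.7 against Appendix 3, reaction by reaction.

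**Step 1: is there a category for Grade 4?**

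| Reaction | Appendix 3 Grade 4 criterion | Highest SAP 9.7 category | Grade 4 shown? |
|---|---|---|---|
| Redness | tissue damage | over 100 mm | no |
| Swelling | tissue damage | over 100 mm | no |
| Pain | emergency room or hospital | severe | no |
| Headache | emergency room or hospital | severe | no |
| Myalgia | emergency room or hospital | severe | no |
| Fatigue | emergency room or hospital | severe | no |
| Fever | above 40 °C | above 40 °C | yes |
| Malaise | none defined (scale stops at Grade 2) | severe | not applicable |

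Appendix 3 defines Grade 4 for 7 of 8 reactions. The SAP matches 1, so 7 − 1 = 6 have no category. The label on the top size band makes it the Grade 3 equivalent. No diameter band can express a tissue-damage criterion.

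**Step 2: does the swelling band follow the swelling grade?** Appendix 3 joins size and function with an *or* at Grades 2 and 3. The grade is therefore the worse of the two, and necrosis is Grade 4 at any size.

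| Diameter | Function or tissue | Appendix 3 grade | SAP band (mm) |
|---|---|---|---|
| 15 mm | prevents daily activity | 3 | >10 to ≤25 |
| 25 mm | no interference | 1 | >10 to ≤25 |
| 30 mm | no interference | 1 | >25 to ≤50 |
| 30 mm | interferes | 2 | >25 to ≤50 |
| 30 mm | prevents daily activity | 3 | >25 to ≤50 |
| 60 mm | prevents daily activity | 3 | >50 to ≤100 |
| 60 mm | necrosis | 4 | >50 to ≤100 |

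The three cases at 30 mm have three different grades and one band, so the grade cannot be recovered from the band.

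**Step 3: boundary.** Appendix 3 Grade 1 starts at 2.5 cm, which is 25 mm. A reading of exactly 25 mm falls in the SAP band that ends at 25 mm, not the one that starts above it. This is a small misalignment, but diameters may be recorded as round numbers.

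**Step 4: scale.** The documents give no rate of functional or Grade 4 reactions, so affected records cannot be counted. For orientation on swelling only, assume that the healthy-adult per-dose rates for swelling of 2.5 cm or more (Appendix 2, Tables 1 and 2: 0.6% to 2.3%) hold here for all four doses. With 115 × 4 = 460 injections, that gives 460 × 0.006 = 2.8 to 460 × 0.023 = 10.6, or about 3 to 11 records. Only those whose functional grade exceeds their size grade would be understated. Smaller swellings with functional impact are outside this figure. With about 115 subjects, one subject moves a percentage by 1/115 = 0.87 points.

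**The case against.** The best defence separates grading from tabulating. The SAP says reactions are graded on the named scale and presented by severity, and a diameter band is a correct report of the measurement. A full-grade table may exist in the table specifications, which are separate documents. That is possible, but it does not cure the text. The only categories the SAP spells out omit these levels, and SAP 9.8 plans no other analyses. If the specifications do use full grades, they and the SAP disagree.

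Three stronger readings are tempting but not supported.

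- *Pain or headache treated with narcotics would be shown as mild, and malaise could be shown as severe although Appendix 3 stops at Grade 2.* This happens only if severity is derived from the SAP's activity wording. If sites record the Appendix 3 grade, as protocol 9.4.6 and 10.1 direct, neither arises. The diary and eCRF are not in the documents.
- *Grade 4 reactions would vanish from the safety report.* Protocol 8.1 lists them among MAEs that stop treatment, with notice to the sponsor within 24 hours. The SAP plans a table of treatment-emergent MAEs leading to discontinuation. In-patient hospitalization is reportable as an SAE whatever its duration.
- *The primary endpoints are certainly untouched, or certainly biased.* Neither can be said. Protocol 8.1 and 10.2 treat a Grade 4 reaction or an emergency room visit as an MAE. Protocol 10.1 and SAP 9.7 describe MAE reporting of reactions that last 8 days or longer and are medically attended, without expressly excluding shorter ones. Pain leading to a short emergency room visit and gone by day 5 shows the tension. Protocol 10.3.2 does not count an emergency visit under 24 hours as hospitalization, so SAE reporting need not catch it.

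**Conclusion.** The categories in SAP 9.7 are wrong as written, and the point is minor. Two defects need no assumption beyond the text: swelling is banded without its functional grade, and six of the seven reactions with a defined Grade 4 have no category for it. The 25 mm boundary is a footnote to these.

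The effect is confined to descriptive reactogenicity tables, which are neither primary nor secondary endpoints. Immunogenicity results do not use them. Stopping decisions rest on the investigator's grading under the protocol, not on SAP tables. The swelling figure above is a pool under a stated assumption, not an error count.

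The MAE reporting wording is a separate matter. It bears on a primary endpoint, the proportion with treatment-emergent MAEs, and the documents do not show whether any event would be missed.

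**What to change.** In SAP 9.7, tabulate each reaction by its Appendix 3 grade: 0 to 4, or 0 to 2 for malaise. Show swelling at the worse of its size grade and functional grade. Keep the millimetre bands as a supplementary table of measured size. State which grade components, if any, the diary or eCRF does not capture, and therefore which grades cannot be derived.

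Separately, reconcile protocol 8.1, 10.1 and 10.2 with SAP 9.7 on when a post-injection reaction is also an MAE, so that sites and programmers apply one rule.

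The tabulation change costs a small text and table-shell edit, after a check of what the diary and eCRF record. Its downside is that some records may be shown at a different grade than under the present categories.

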9.8 Other Analyses

No other analyses are planned.

9.9 Interim Analysis

A preliminary analysis may be performed to assess the primary immunogenicity objective of the SPR at Week 20 after approximately 50 subjects have completed their Week 20 visit. The scope of the analysis is limited to the estimates of the SPR at Week 20. Limited demographic and safety data may be presented along with the SPR estimates. The list of analyses for this interim analysis will be highlighted in the Table of Contents of Tables, Figures and Listings document.

9.10 Reporting Output

All outputs will be produced using SAS® version 9.3 or later. The REPORT procedure will be used to produce all tables and listings whenever possible. The SGLOT procedure will be used to produce all figures whenever possible. All statistical appendices (supportive SAS output) will be output directly from the appropriate SAS procedure.

Post-text tables, listings, and statistical appendices will be produced as RTF files using output delivery system (ODS) and Times New Roman or a similar font size 8 or larger. Data will be presented in RTF tables with data in individual cells. Figures will be produced as RTF files using ODS and simplex font. For all outputs, the page numbering will be applied to ensure that when the RTF files are combined, the page numbering remains fixed.

All tables, listings and statistical appendices will be produced to landscape orientation and will be incorporated into a Word 2010 or later document (margins: top 1.5", left, right and bottom 1") using 8pt font or larger.

Vaccine name for tables and figures will be as follows:

- HEPLISAV-B

10.0 REVISION HISTORY

Version	Date	Author	Comments/Rationale for Revision
1.0	25FEB2020	██████████	New Document
2.0	02SEP2020	██████████	Update for Protocol Amendment 4
2.1	15SEP2020	██████████	COVID-19 Specific Update [1] on Major Protocol Deviations/PP Population definition: “vaccine given outside protocol specified visit window at Weeks 4, 8 and 16 (± 7 days)” are not Considered as Major Protocol Deviations for PP Population Exclusion Purpose.

12.0 LIST OF TABLES

List of tables will be provided in a separate Table of Contents of Tables, Figures and Listings document.

13.0 LIST OF FIGURES

List of figures will be provided in a separate Table of Contents of Tables, Figures and Listings document.

14.0 LIST OF PATIENT DATA LISTINGS

List of listings will be provided in a separate Table of Contents of Tables, Figures and Listings document.
